5.2 Demography and baseline characteristics

Age, height, weight, medical history, PAH classification, WHO functional class, Vital signs, oxygen saturation, hemodynamics (invasively assessed by right heart catheterization and by echocardiography), laboratory, quality of life.

5.3 Secondary analysis

5.3.1 Secondary efficacy endpoints

will be tested hierarchically:

- change of cardiac index at rest (baseline to 24 weeks)
- change of total pulmonary resistance (baseline to 24 weeks)
- change of diffusion capacity of the lung (baseline to 24 weeks)
- change of 6-minute walking distance (baseline to 24 weeks)

- change of WHO functional class (baseline to 24 weeks)
- change in QoL (SF-36, physical summation score; baseline to 24 weeks)

The following parameters will be assessed in every patient according to the visits schedule and analyzed as **exploratory variables**. Changes between groups will be compared by student's t-test or Welch-test if variances are not equal. Nonparametric data will be compared by Wilcoxon-Mann-Whitney test. Frequency data will be compared with chi-square tests. Exploratory endpoints will be analyzed as change from baseline to 12 and 24 weeks as available per assessment schedule. According to the study protocol, patients were encouraged to perform their final assessment visit in case of any premature termination of study treatment or study participation.

QoL assessed by the SF-36 questionnaire

Short form health survey 36, including 2 summation scores and 8 subscores.

QoL will be assessed using the SF 36-questionnaire that will be handed out to the patients. Scoring will be carried out according to the test manual.

The SF-36 consists of eight scaled scores, which are the weighted sums of the questions in their section. Each scale is directly transformed into a 0-100 scale, i.e. a score of zero is equivalent to maximum disability and a score of 100 is equivalent to no disability. The eight sections are: vitality; physical functioning; bodily pain; general health perceptions; physical role functioning; emotional role functioning; social role functioning; mental health.

WHO functional class

Analysis of changes between baseline and first/second follow-up.

Lung function and lung diffusing capacity

- FEV1 (forced expiratory volume in 1 second), TLC (total lung capacity), DLCO (diffusing capacity of the lung)

Echocardiography

- systolic pulmonary arterial pressure (sPAP, mmHg), right ventricular area (RV-area, cm²), and right atrial area (RA-area, cm²), tricuspid annular plane systolic excursion (TAPSE), left ventricular eccentricity index (LV-EI), RV-pump function and LV-pump function (LV-EF, %).

Analyses of blood samples

Venous blood will be analyzed to determine:

- NT-pro BNP

Blood for blood gas analyses

- oxygen partial pressure, carbon dioxide partial pressure, oxygen saturation of the blood (SpO_2), pH values, bicarbonates, base excess

Pulmonary hemodynamics by right heart catheterization

- sPAP, mPAP, diastolic pulmonary artery pressure (dPAP), pulmonary artery wedge pressure (PAWP), right atrial pressure (RAP), cardiac output and ejection fraction (CO), central venous saturation, via blood gas analysis from pulmonary artery (SvO_2)

Clinical worsening will be defined as time to first event out of:

- worsening of WHO functional class
- deterioration of 6MWD >15% compared to baseline
- need of initiation of targeted PAH treatment
- hospitalization due to worsening of right heart function
- all cause death or lung-transplantation
- atrial septostomy

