All secondary analyses will be exploratory and will be considered descriptively. Secondary parameters at baseline and during follow-up will be compared between groups comparing the difference between baseline and follow-up visits. Data will be displayed by means and standard deviations, medians and variances with respective 95% confidence intervals. p-values <0.05 will be considered as statistically significant.

Secondary endpoints will be statistically analyzed by a hierarchical testing strategy using the two-sided student's t-test with comparison of the differences between riociguat (MK-4836) and placebo.

The sequential testing procedure will be performed for these six secondary efficacy variables, strictly in the order listed

- change of cardiac index at rest (baseline to 24 weeks)
- change of total pulmonary resistance (baseline to 24 weeks)
- change of diffusion capacity of the lung (baseline to 24 weeks)
- change of 6-minute walking distance (baseline to 24 weeks)
- change of WHO functional class (baseline to 24 weeks)
- change in QoL (SF-36, physical summation score; baseline to 24 weeks)

It is assumed that WHO functional class will either remain the same, improve by one or two categories, or deteriorate by one category in most cases. A change score (baseline minus end of study) will be calculated, which could go from -3 (class IV at baseline and class I at end of study) to +4 (class I at baseline, death at end of study), but in practice for those patients still alive at the end of the study it will most likely range from -2 to +1.

EudraCT: 2021-001633-40	Version 1.7 15.01.2025	ESRA
-------------------------	---------------------------	------

Exploratory endpoints

Further outcome parameters will be tested exploratory and reported with 95% confidence intervals of the difference between changes in the intervention and placebo group, mean and standard deviation of the mean. Parameters will be analyzed as change from baseline to 24 weeks riociguat (MK-4836) vs. placebo; if available as per visit and assessment schedule, changes between baseline and 12 weeks will also be analyzed.

Patients who withdraw from the study will be asked to complete a final examination which will be included in the data analysis.

Parameters for explorative data analysis include

WHO functional class (baseline to 12 weeks)

Echocardiography

- sPAP, RV-area and RA-area, TAPSE, LV-EI, RV-pump function and LV-EF.

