7.6 Secondary analyses

7.6.1 Efficacy

All secondary analyses will be exploratory and will be considered descriptively. Secondary parameters at baseline and during follow-up will be compared between groups comparing the difference between baseline and follow-up visits. Data will be displayed by means and standard deviations, or in case of non-normally distributed data with medians and variances. Changes will be displayed with means and standard deviations with respective 95% confidence intervals.

Secondary endpoints will be statistically analyzed by a hierarchical testing strategy using the two-sided student's t-test with comparison of the differences between riociguat (MK-4836) and placebo. p-values <0.05 will be considered as statistically significant.

The sequential testing procedure will be performed for these six secondary efficacy variables, strictly in the order listed

- change of cardiac index at rest (baseline to 24 weeks)
- change of total pulmonary resistance (baseline to 24 weeks)
- change of diffusion capacity of the lung (baseline to 24 weeks)
- change of 6-minute walking distance (baseline to 24 weeks)
- change of WHO functional class (baseline to 24 weeks)
- change in QoL (SF-36, physical summation score; baseline to 24 weeks)

Further outcome parameters will be tested exploratory and reported with 95% confidence intervals of the difference between changes in the intervention and placebo group, mean and standard deviation of the mean. Normally distributed data will be compared by two-sided student's t-tests or Welch-test in case of unequal variances. Non-normally distributed data will be analysed by nonparametric analysis methods such as the Wilcoxon-Mann-Whitney test. Frequency data will be compared by Chi square test, if preconditions are met. Parameters will

be analyzed as change from baseline to 24 weeks riociguat (MK-4836) vs. placebo; if available as per visit and assessment schedule, changes between baseline and 12 weeks will also be analyzed.

Patients who withdraw from the study will be asked to complete a final examination which will be included in the data analysis.

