7.6.3 Exploratory analysis

Changes between baseline and 12 weeks, and between baseline and 24 weeks will be compared between groups by two-sided student's t-tests or Chi-square tests. For parameters see section 5.2.

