7.8 Interim analyses

Not available

8 Deviations from the original protocol

The study was ended prematurely, leading to a sample size reduction to 35 patients (planned 70 patients).

The study was terminated early due to a strategic decision of MSD/Merck:

“After reviewing the timelines, remaining payments, and considering the changing landscape and altered feasibility of this study, a strategic prioritization was made to select this study for early termination.”

As a result of this decision, the final sample size reached 50% of the originally planned enrolment (n= 35). All statistical analyses will be conducted based on the available data at the time of study cessation. The reduction in sample size may limit the statistical power, particularly given the double blinded two-armed design of the study. According to the study protocol, patients were encouraged to perform their final assessment visit in case of any premature termination of study treatment or study participation. This data will be included into the final analysis according to the intention-to-treat principle.

Subgroup analyses may not be performed due to insufficient sample size.

9 Interpretation of results

Interpretation of data is limited by the early termination of the whole trial. This led to a reduction of sample size to 35 patients in total instead of per group, and to a premature study termination in a subset of patients. As the treatment effect is anticipated to be less distinct in a shorter period of time in the verum group and worsening of clinical parameters is expected to be less pronounced in the control group, early study termination will reduce the effect size and does therefore not bear the risk of overestimation of the clinical effects of the study treatment. A shorter study duration is expected to reduce the statistical power (reduction of sample size and effect size).

Safety data will comprise of less investigational medicinal production exposition than planned. As the study medication is already an approved treatment and extensive data on safety and tolerability is already available, a substantial impact on safety and tolerability results of the study is not anticipated.

Due to the reduced sample size, subgroup analyses such as centre effects may not be further analysed as sample sizes for each center and for hemodynamics subgroups are not high enough.

10 Data problems

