Analysis of PVR distribution identified an outlier at visit 3, which could be corrected by calculation of PVR from the formula $PVR = (mPAP - PAWP) / CO * 80$

PVR was therefore recalculated for all values at visit 3.

11 Software

Data analysis with SPSS V29, IBM Somers, New York.

12 References

NA

13 Appendices – List of Tables

All tables with mean \pm standard deviation or n and % for frequency data.

Tables with comparisons between groups will additionally include p-values and 95% confidence intervals.

Table 1. Demographics and Baseline Characteristics for the whole dataset and by group.

(table may be split for better readability)

Female sex no. [%]

Age [years]

Height [cm]

Weight [kg]

PH duration [months]

Vital

signs

Systolic blood pressure

Diastolic blood pressure

SpO₂ [%]

Heart rate

WHO FC no. [%]

I

II

III

IV

PAH Etiology

Idiopathic

Heritable

CTD-associated-PAH

Other

Concomitant diseases

Blood gas analysis

SaO₂ [%]

PaO₂ [mmHg]

PaCO₂ [mmHg]

pH

Bicarbonates

Hemodynamics at rest

RAP [mmHg]

sPAP [mmHg]

dPAP [mmHg]

mPAP [mmHg]

PAWP [mmHg]

CO [l/min]

CI [l/min/m²]

PVR [WU]

SvO₂ [%]**6MWD**

6MWD [m]

SpO₂ [%] test end

Borg dyspnea score

Short Form-36 Health Survey

Physical functioning

Physical role function

Pain

General health perception

Vitality

Social functioning

Emotional role function

Mental well-being

Physical summation score

Mental summation score

Echocardiography at rest

Estimated sPAP [mmHg]

RA area [cm²]RV area [cm²]

TAPSE [cm]

LV-EI

Left ventricular ejection fraction [%]

Lung function

FVC [L]

FEV1 [%predicted]

TLC [%predicted]

Residual Volume [%predicted]

DLCO % predicted

DLCO VA % predicted

Laboratory

Hemoglobin [g/dl]

Creatinine [mg/dl]

Urea [mg/dl]

Uric acid [mg/dl]

SGPT [U/l]

CRP [mg/l]

NTproBNP [pg/ml]

Table 2**Comparison of changes between groups****WHO FC Change (Visit 1-2)**

Improvement (- 1)

Worsening (+1)

Unchanged

Blood gas analysis

SaO2 [%]

PaO2 [mmHg]

PaCO2 [mmHg]

pH

Bicarbonates

Hemodynamics at rest

RAP [mmHg]

sPAP [mmHg]

dPAP [mmHg]

mPAP [mmHg]

PAWP [mmHg]

CO [l/min]

CI [l/min/m²]

TPR mmHg [min l- 1]

PVR [WU]

SvO2 [%]

6MWD

6MWD [m]

Short Form-36 Health Survey

Physical functioning

Physical role function

Pain

General health perception

Vitality

Social functioning

Emotional role function

Mental well-being

Physical summation score

Mental summation score

Echocardiography at rest

Estimated sPAP [mmHg]

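### The SAP does not fix one suitable test for the exploratory change in WHO functional class; the natural reading is an unordered chi-square test whose usual condition 35 patients will almost never meet

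*SAP*

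**What the plan says.** Four places in the SAP bear on the exploratory change in WHO functional class.

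- **Section 13, Table 2** (between-group comparison of changes) has a block headed "WHO FC Change (Visit 1-2" with three rows: improvement (-1), worsening (+1) and unchanged. The introduction to the tables describes frequency data as n and %, and says that between-group tables also carry p-values and confidence intervals.
- **Section 5.3.1** gives three routes for exploratory changes: a t-test or Welch test; "Nonparametric data will be compared by Wilcoxon-Mann-Whitney test"; and "Frequency data will be compared with chi-square tests". It lists WHO functional class as an exploratory variable but does not say which route it takes.
- **Section 7.6.1** repeats the routes with a condition: "Frequency data will be compared by Chi square test, if preconditions are met". It names no alternative if they are not met.
- **Section 7.6.3** says that 12-week and 24-week changes are compared "by two-sided student's t-tests or Chi-square tests". It has no rank test and no condition. It refers to section 5.2 for the parameters, and that list includes WHO functional class.

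The 24-week change is also the fifth of six hierarchical secondary endpoints. SAP 7.6.1 tests those by the "two-sided student's t-test with comparison of the differences between riociguat (MK-4836) and placebo". On sample size, SAP section 8 says that "the final sample size reached 50% of the originally planned enrolment (n= 35" patients. Protocol 10.3.1 treats WHO functional class change as a signed score and expects most patients to stay the same, "improve by one or two categories, or deteriorate by one category in most cases".

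**The concern.** WHO functional class is ordinal, and so is its change. Pearson's chi-square statistic is the same however the three columns are ordered. More improvement on riociguat and more worsening on placebo therefore get no credit for pointing the same way.

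The test is also a large-sample approximation, and the SAP itself makes it conditional in 7.6.1. With 35 patients in three categories, most of them probably unchanged, the usual condition will rarely hold. The SAP does name a fallback for paired frequency data (7.6.2.1), but none for comparisons between arms. The analyst would then have to choose a test after seeing the table, or use one that fails the condition.

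WHO functional class is one of few efficacy measures at week 12. The schedule has no catheterization, echocardiography, lung function or SF-36 at that visit. At stake are the clarity and efficiency of one exploratory p-value, not the trial's main conclusion.

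**Working it through.** **The plan's own figure.** The documents state no power for WHO functional class. Their only power figure is for pulmonary vascular resistance: d = 30/34.5 = 0.87, 29 per group, two-sided 0.05, t-test. It reproduces at 90.2% and has no bearing on this point.

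**Inputs.** N = 35 (SAP section 8); 1:1 allocation (SAP 1.2); two-sided alpha 0.05 (SAP 7.5). Arm sizes are not given, so 17 placebo and 18 riociguat are assumed. Category shares are assumed throughout, because the documents give none.

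**Step 1: expected counts.** For a category with m patients in total, the smaller arm's expected count is 17 × m/35.

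- m = 10: 17 × 10/35 = 4.86, below 5.
- m = 11: 17 × 11/35 = 5.34, above 5.

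All three categories thus need at least 11 patients, 3 × 11 = 33 of 35. Only totals of 11, 11, 13 or 11, 12, 12 in some order qualify. If each category had probability 1/3 in both arms, the chance is

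3 × [35!/(11! 12! 12!) + 35!/(11! 11! 13!)] / 3^35 = 13%.

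In the four ordered-shift scenarios of step 2, it is 0.03% or less.

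**Step 2: power when the shift is ordered.** All possible 2 × 3 tables at 17 and 18 patients were enumerated exactly. The tests were:

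- Pearson chi-square, Σ(O − E)²/E, on non-empty categories minus 1 degrees of freedom;
- Wilcoxon-Mann-Whitney with midranks, z = (W − n₁(N+1)/2)/√V, where V = (n₁n₂/12) × [(N+1) − Σ(t³ − t)/(N(N−1))] and t are the category totals.

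| Placebo (improved/unchanged/worsened, %) | Riociguat | Chi-square | Wilcoxon |
|---|---|---|---|
| 10/75/15 | 35/60/5 | 36% | 48% |
| 10/70/20 | 40/55/5 | 51% | 64% |
| 15/65/20 | 45/50/5 | 46% | 59% |
| 15/75/10 | 35/62/3 | 22% | 32% |
| 10/75/15 (no effect) | 10/75/15 | 3.8% | 4.7% |

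Swapping which arm has 17 patients moves these figures by about one point.

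Over a wider grid (eight control distributions, proportional-odds shifts with odds ratios 2 to 8), the Wilcoxon gain is about 4 to 16 points: roughly 4 to 6 at odds ratio 2, 8 to 10 at 3, 10 to 13 at 4, and 7 to 16 at 6 to 8. With 15 evaluable patients per arm it is about 3 to 16 points.

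**Step 3: power when the shift is not ordered.**

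| Pattern | Placebo | Riociguat | Chi-square | Wilcoxon |
|---|---|---|---|---|
| Only improvement changes | 10/80/10 | 35/55/10 | 34% | 28% |
| Only worsening changes | 10/60/30 | 10/85/5 | 43% | 32% |

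If both improvement and worsening rise on the drug, the Wilcoxon test has little power by design; in one such case it lost 36 points to chi-square.

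**The case against.** A reader might infer that the SAP prescribes chi-square for this variable. It does not. Section 5.3.1 lists a t-test and the Wilcoxon-Mann-Whitney test beside chi-square, Protocol 10.3.1 treats the change as a numeric score, and Table 2 is a display layout. A t-test on the score would lose almost nothing: 47%, 63%, 59% and 32% in the four ordered scenarios. This stands as far as it goes. But the layout makes these frequency data, and section 7.6.3 drops the rank test, so the text does not settle the choice.

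A reader might also infer a fixed power loss of, say, 10 to 13 points. The documents cannot support one. The gain depends on assumed rates and reverses for one-ended effects.

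Nor can it be said that chi-square breaks a rule in the SAP or inflates false positives. The SAP never defines its preconditions; expected counts of at least 5 is the usual convention. Chi-square was conservative in the null case above (3.8%).

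Finally, the expectation of two-class improvement in Protocol 10.3.1 concerns the end of the study. It does not show that Table 2, at week 12, omits an expected outcome. Listing all observed values is simply safer.

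**Conclusion.** The point holds as a gap in specification. Sections 5.3.1, 7.6.1 and 7.6.3 give different rules for the same kind of data, none assigns a test to WHO functional class change, and no between-group fallback is named. The natural reading is a test that ignores the ordering and whose usual condition would almost never be met with 35 patients. This part needs only the arm sizes and the expectation that most patients stay in their class.

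The power difference, about 4 to 16 points in favour of the Wilcoxon-Mann-Whitney test, rests on assumed rates and on an effect that shifts patients consistently towards improvement. It is an illustration, not a property of the trial.

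Impact is low. The comparison is exploratory, and the 24-week hierarchical endpoint is tested separately on a score that keeps the order. This is a cheap improvement.

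**What to change.** In SAP 5.3.1, 7.6.1 and 7.6.3, take WHO functional class change out of the chi-square rule and state: the exploratory change in WHO functional class (end minus baseline, full ordinal score) will be compared between groups by the tie-corrected Wilcoxon-Mann-Whitney test.

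In Table 2, show n (%) by arm for every observed change value instead of three fixed rows. For nominal frequency data, name Fisher's exact test when any expected count is below 5, so that the condition in 7.6.1 has a definition and a fallback.

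State the sign of the change once. Table 2 codes improvement as -1, which is end minus baseline. Protocol 10.3.1 describes baseline minus end of study but scores a move from class IV to class I as -3.

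The cost is SAP wording and a procedure already planned for other variables; no new data are needed. There are two small downsides: less power than chi-square if the effect is one-ended or non-monotone, and a p-value with no accompanying difference in proportions. The fuller n (%) table lets a reader see both.

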5.4 Tolerability, safety and survival

The safety analysis will be performed in the population valid for safety. All tabulations will be descriptive only. Tables will be produced for drug-related adverse events and serious adverse events. Further tables will be produced for serious adverse events.

Mortality will be summarized descriptively. Any deaths in the study period (until survival follow-up) will be listed, with day of death relative to start and stop of study drug and cause of death.

Safety variables include:

Electrocardiogram (ECG)

Vital signs: Blood pressure, heart rate/pulse, oxygen saturation

Hemodynamics: Cardiac Output, SvO_2 (during RHC)

Echocardiography

Clinical laboratory investigations

Concomitant medication

Concomitant diseases

Adverse events

Clinical worsening was defined as time to first event out of:

- worsening of WHO functional class
- deterioration of 6MWD >15% compared to baseline
- need of initiation of targeted PAH treatment
- hospitalization due to worsening of right heart function
- all cause death or lung-transplantation
- atrial septostomy

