8.3 Study Phases and Visits

8.3.1 Screening Phase

Patients who sign the informed consent form to participate in the medical trial will undergo the screening examinations: medical history, demographics, checking of in- and exclusion criteria, physical and weight examination, vital signs (blood pressure, heart rate, SpO₂), lung function test (body plethysmography and diffusion capacity), blood gas analysis (BGA), echocardiography at rest, right heart catheterization with continuous 12-lead ECG at rest, clinical laboratory, including pregnancy test (only WOCBP), survey of concomitant medication and diseases and recording of adverse events. Measurements/assessments taken during screening visit will be recorded as baseline values for study assessment of endpoints unless described otherwise.

The right heart catheterization should not be older than 1 month at screening or not older than 6 months if the patient had no signs of clinical changes defined as change of 6MWD >10%, WHO-FC change or >30% change in NT-proBNP. RHC must have been measured in the participating

EudraCT: 2021-001633-40	Version 1.7 15.01.2025	ESRA
-------------------------	---------------------------	------

center under standardized conditions. Patients without recent RHC fulfilling the above-mentioned criteria, will receive a RHC at screening, be before the beginning of the intervention. Baseline will be within 28 days after screening.

If, due to organisational reasons, echocardiography cannot be performed at Baseline, it can be performed during Screening period and it can be used as baseline value. Echocardiography cannot be performed after baseline.

8.3.2 Visit 1 Baseline / Randomization - Day 1

Baseline visit may be performed according to the hospital's routine practice as in-hospital stay.

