9.2 Period of Observation and Documentation

All AEs reported by the subject or detected by the investigator, will be collected during the trial and must be documented on the appropriate pages of the CRF. AEs must also be documented in the subject's medical records.

In this trial, all AEs that occur after first administration of the IMP up to the last visit (i.e. follow-up visit) will be documented on the pages provided in the CRF. AEs will be assessed by the investigator using no-leading questions or observed during any visit during the whole study. The patient should be motivated to report any AEs by phone to the investigator occurring in between study visits. All subjects who have AEs, whether considered associated with the use of the trial medication or not, must be monitored to determine the outcome. The clinical course of the AE will be followed up until resolution or normalization of changed laboratory parameters or until it has changed to a stable condition.

Each event should be described in detail along with start and stop dates, severity, relationship to investigational product, action taken and outcome.

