QoL assessed by the short form of the medical outcome questionnaire (SF-36 questionnaire)

- (mental summation score as well as the 8 sub-scores)

Lung function and lung diffusing capacity

- FEV1 (forced expiratory volume in 1 second), TLC (total lung capacity), DLCO (diffusing capacity of the lung)

Blood for blood gas analyses:

- oxygen partial pressure, carbon dioxide partial pressure, SpO₂, pH values, bicarbonates, base excess

Analyses of blood samples:

- NT-pro BNP

Pulmonary hemodynamics by right heart catheterization:

- CI, sPAP, mPAP, dPAP, PAWP, RAP, PVR, CO, SvO₂

EudraCT: 2021-001633-40	Version 1.7 15.01.2025	ESRA
-------------------------	---------------------------	------

Sensitivity analyses

Sensitivity analyses will be performed to investigate the effect on patients with higher vs. lower PVR and higher vs. lower mPAP. A multiple imputation strategy will be implied and analyzed for the primary endpoint.

Safety analysis

The safety analysis will be performed in the population valid for safety. All tabulations will be descriptive only. Tables will be produced for drug-related treatment-emergent adverse events and serious adverse events. Further tables will be produced for serious and/or drug-related treatment-emergent adverse events.

Mortality in the 24-week period of the study will be summarized descriptively. Any deaths in the study period will be listed, with day of death relative to start and stop of study drug and cause of death.

The safety evaluation of laboratory data will include:

listings of laboratory data out of normal range, evaluation of the significance if they are out of normal range, descriptive analysis of continuous laboratory parameters and their changes from baseline by visit and treatment group. Vital signs will be summarized by visit and treatment group.

Clinical worsening (as exploratory safety endpoint) will comprise of the following parameters:

- worsening of WHO functional class
- deterioration of 6MWD >15% compared to baseline
- need of initiation of targeted PAH treatment
- hospitalization due to worsening of right heart function
- all cause death or lung-transplantation
- atrial septostomy

Biometric analysis will be defined in the statistical analysis plan which has to be authorized before data base lock by the biometrician and the Coordinating Investigator.

EudraCT: 2021-001633-40	Version 1.7 15.01.2025	ESRA
-------------------------	---------------------------	------

11 Data Management

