7.6.2.1 Adverse events

Tables will be produced for adverse events with a frequency $\geq 5\%$, drug-related adverse events and serious adverse events. Serious adverse events, adverse events with a frequency $\geq 5\%$ and drug-related adverse events will be displayed separately. In case of paired frequency data, analyses will be performed with McNemar Bowker test, or Wilcoxon signed rank test if preconditions are not met. Differences between therapy groups will be displayed by tabulation of results.

Mortality in the 24-week period of the study will be summarized descriptively. Any deaths in the study period will be listed, with day of death relative to start and stop of study drug and cause of death.

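### The SAP's adverse-event tables omit the protocol's treatment-emergent restriction, and the documents disagree on when recording starts, so pre-dose events can enter the by-arm counts

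*SAP*

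**What the plan says.** **Tables.** Protocol 10.3.1 (Safety analysis) plans two sets: "Tables will be produced for drug-related treatment-emergent adverse events and serious adverse events", then "Further tables will be produced for serious and/or drug-related treatment-emergent adverse events". SAP 5.4 has the first sentence as "Tables will be produced for drug-related adverse events and serious adverse events" and shortens the second to serious events only. The term treatment-emergent is gone from both. SAP 7.6.2.1 adds a table by frequency: "Tables will be produced for adverse events with a frequency $\geq 5\%$, drug-related adverse events and serious adverse events". It then says "Differences between therapy groups will be displayed by tabulation of results". Table 3 in the SAP appendix lists the same three kinds of table. None of these places gives a date from which events count, and neither document defines treatment-emergent.

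**Deviations.** SAP section 8 covers the early stop, the reduced sample size and the subgroup analyses. It does not mention the adverse-event tables.

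**Collection.** Protocol 8.3.1 includes among the screening examinations "survey of concomitant medication and diseases and recording of adverse events". The schedules in Protocol 8.1 and SAP section 4 mark adverse events at both Screening and Visit 1. Protocol 9.2 says something different: "all AEs that occur after first administration of the IMP up to the last visit (i.e. follow-up visit) will be documented" in the CRF.

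**The concern.** A safety table by arm should count what happened after treatment began. The safety set in SAP 2.1 requires at least one dose, but that selects patients, not events. A dosed patient's screening event would pass that test. With the onset restriction removed, nothing in the SAP keeps such an event out of the tables. The SAP also reproduces a schedule that records events before dosing, and it does not carry over the limit in Protocol 9.2.

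Safety and tolerability is a stated secondary objective (SAP 1.1), and its adverse-event evidence consists of descriptive counts. With 35 patients, a few events from before the first dose would be visible in those counts. A reader comparing the two documents would also find a change to a planned safety analysis that is not declared.

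**Working it through.** The plan states no figure on this point, so there is none to reproduce. The check has three steps.

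**1. When does recording start?**

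| Source | Start of recording |
|---|---|
| Protocol 8.1 and SAP section 4 (schedules) | Screening, and again at Visit 1 |
| Protocol 8.3.1 | Screening |
| Protocol 8.3.2 | Visit 1 assessments, described ahead of randomisation and the handing out of study drug |
| Protocol 6.6 | Illness present at consent is medical history; what first appears or worsens during the trial is an adverse event for the CRF |
| Protocol 9.1.1 | An adverse event is tied in time to the use of a drug |
| Protocol 9.2 | After first intake |

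The first four place recording before the first dose. The last two place it after. The texts do not resolve this.

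**2. Which tables are exposed, if recording began at Screening?**

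- *Drug-related events:* hardly at all. Protocol 9.1.6 requires a rating of possible, probable or definite, and an event before any drug should not receive one.
- *Serious events:* exposed. The protocol's first sentence leaves it unclear whether treatment-emergent also governs serious events; its second arguably does cover them.
- *Events at the 5% cut-off:* exposed. The SAP added this table, so no protocol restriction was removed from it, but it has no onset window.

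**3. How large could it be?**

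Inputs: screening of up to 28 days (Protocol 5.1), 24 weeks of treatment = 168 days, follow-up at 30 days, and 35 patients (SAP sections 3 and 8).

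Pre-dose share of the recording window = s / (s + 168 + 30), where s is the number of screening days:

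- s = 0: 0%
- s = 14: 14/212 = 6.6%
- s = 28: 28/226 = 12.4%

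At s = 28, the ±14-day windows on the week 24 visit and the follow-up call give 28/(28 + 182 + 44) = 11.0% to 28/(28 + 154 + 16) = 14.1%. Patients whose treatment was cut short by the early stop would have a larger share; the documents do not give their durations.

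Patients needed for a term to reach the 5% cut-off:

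- Applied to all 35: 0.05 × 35 = 1.75, so two patients.
- Applied per arm, assuming 17 and 18: 1/17 = 5.9% and 1/18 = 5.6%, so one patient.

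The SAP does not say which base applies and does not give the actual split. SAP 7.6.2.1 uses at least 5% and Table 3 uses more than 5%. For 35, 17 or 18 patients this makes no difference, because 5% is not a whole number of patients (1.75, 0.85 and 0.9).

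**The case against.** The strongest reply is that Protocol 9.2 is the section dedicated to the period of observation, and it starts CRF documentation at first intake. If sites followed it, the database holds no pre-dose events and the missing term changes nothing. The definition in 9.1.1 points the same way. This stands as a possibility. It does not settle the matter, because the schedule, 8.3.1 and 6.6 instruct sites otherwise and the SAP carries the schedule forward.

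Several limits on the size also stand. Twenty-eight days is a maximum, and Screening and Visit 1 may fall in the same hospital stay. The screening catheterisation is skipped when a valid recent one exists, and planned admission for elective catheterisation is not reported as a serious event (Protocol 9.1.2). If the cut-off is per arm, one on-treatment event also creates a row, so that sensitivity comes from the small sample rather than from the missing term.

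A reader might infer two stronger things. The first is that pre-dose events will be counted. The documents do not support this, since 9.2 may have kept them out of the CRF. The second is that the arm comparison is biased towards one treatment. That is not supported either. These events precede treatment in a randomised, blinded trial, so they are expected equally in both arms. They leave the expected difference in event counts unchanged, pull the ratio towards one, and add chance variation.

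**Conclusion.** The point holds in a limited form. The SAP omits a restriction that the protocol states, sets no counting window, and does not declare the change. If events were recorded from Screening, as the schedule directs, those before the first dose can enter the serious-event table and the 5% table. If Protocol 9.2 was followed, the number is zero.

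The size is 0% to about 12% of the recording window at nominal visit times. One patient (per arm, near-equal split) or two (overall) would be enough to put a term in the 5% table. This assumes that all 35 patients were dosed.

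The tables are descriptive, so no hypothesis test and no efficacy result is affected. This is a free improvement to the SAP, not a defect that threatens the trial's conclusions.

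**What to change.** - In SAP 5.4, 7.6.2.1 and Table 3, restrict all adverse-event and serious-event tables to treatment-emergent events. Define these as events with onset or worsening from first intake of study medication to the safety follow-up, and say how an event dated on the day of first intake is assigned.
- List any pre-dose events separately, outside the arm comparison.
- Reconcile Protocol 9.2 with the visit schedule. As enrolment has ended, state in SAP section 8 which rule the CRF followed.
- In the same edit, say whether the 5% cut-off is per arm or overall, and use one form of it (at least 5%, or more than 5%).

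The cost is a definition, a few words in three places and one filter on onset date. Protocol 9.2 already asks for start and stop dates for each event, so no new data should be needed. If no pre-dose events were recorded, the filter changes nothing; if some were, it restores the restriction the protocol planned.
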